3.6 COPD Assessment Tool (CAT)

The COPD assessment tool (CAT) consists of 8 questions each scored from 0-1 am very happy to 5-1 am very sad. The assessment results in a total score which is determined but summing the responses to all the questions, this generates a score ranging from 0 to 40. The higher the score the greater the impact of the disease.

If one or two components are missing the total score can still be generated with the missing observation be set to the average of the non-missing scores¹.

If more than two responses are missing then the CAT cannot be calculated and will be left as a missing value.

The redcap data base has a field for total score 'cat_total_score' however this should not be used as this field is the sum of responses to the 8 questions and does not account for any missing observations. The total score has been calculated to take missing observations into account.

3.7 Spirometry

The way spirometry data has been captured changed over the course of the trial. Initially there was space to record up to 3 readings for each of the spirometry markers however this was changed to capture only the maximum value.

For the purpose of the analysis described here we will use only the maximum value captured at the post-bronchodilation point.

Version No 2.1

Effective Date 27Jun2025

4. List of Analyses

4.1 Recruitment

A standard accrual plot showing the cumulative total over time with a planned recruitment line shown to illustrate the projected target. In addition a plot showing the number of participants recruited each quarter.

4.2 Attendance/Compliance

For each visit the number and percent of participants will be presented and broken down by treatment.

Study drug compliance will be assessed and recorded by trial personnel by checking the dose indicators on the medication returned at the one month, six month and twelve-month (end of study).

Absolute compliance is calculated as: number of doses dispensed - number of doses returned

Percentage compliance is calculated as:

$$\frac{(number\ of\ doses\ dispensed-number\ of\ doses\ returned)}{(final\ visit\ date\#-dispensing\ visit\ date)}*100$$

where a person has terminated the trial early, the timeframe over which the drugs should have been taken will be determined up to the point at which they withdrew from the trial so the change of status date will be used in place of the final visit date.

A 50% threshold for compliance will apply for the duration of the study.

4.3 Baseline Data

Presentation of baseline characteristics of those participating in the trial will be split by treatment allocation for the following: demographic variables (age, sex, ethnicity, socioeconomic status), employment history (currently employed, history of occupational dust exposure), lifestyle (smoking history, alcohol history), physical examination, relevant medical/surgical history, vital signs, pregnancy test/contraception, exacerbations, ECG, spirometry, concomitant medications, SGRQ-C, COPD Assessment, blood tests, sputum sampling, modified MRC breathlessness score.

A table will be presented separately from the baseline table showing the distribution of participants according the variables used in the minimisation: prior ICS (yes/no) and prior long-term macrolides (yes, no). These variables are all expressed in a binary form and will be presented as number of participants and percentage of each treatment allocation.

Where variables are categorical (including binary) numbers and percentages will be presented. Where variables are continuous the following information will be presented: number, number missing, mean, standard deviation, minimum, lower quartile, median, upper quartile and maximum.

4.4 Primary Outcome

A comparison between treatment arms for baseline to 1-year change (expressed in log units) in colony forming units per ml will be analysed using a two-sample t-test. The change will be calculated as: $log(CFU\ per\ mL\ at\ 12\ months) - log(CFU\ per\ mL\ at\ baseline)$

Version No 2.1

Effective Date 27Jun2025

Descriptive statistics will be presented by treatment arm at each time point in addition to the baseline to 1-year change, and the pattern of change over time shall be presented graphically.

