The FLAME trial, on the other hand undertook a randomised, double-blind non-inferiority trial⁸. Patients who had COPD with a history of at least one exacerbation during the previous year were randomly assigned to receive, by inhalation, either the LABA plus the LAMA once daily or the LABA plus the inhaled glucocorticoid fluticasone twice daily. The trial showed that the LABA-LAMA group was more effective in preventing exacerbations than the LABA-ICS group (p <0.001) and was associated with lower incidence of community-acquired pneumonia (p= 0.02). This reaffirms that LABA-LAMA could be a safe alternative if triple therapy is not deemed suitable for some reason in COPD patients with frequent exacerbations.

The main reported risk of ICS in COPD is that of increase risk of pneumonia and hence should be used in accordance to available protocols of COPD management. Despite this data drawn from the Adelphi Respiratory Disease Specific Program, a large multinational (France, Germany, Italy, Spain, UK, USA) cross-sectional survey generating real-world data based on actual clinical practice, showed there is still overuse of inhaled corticosteroids in all groups of disease severity in COPD (33% in Stage A, 38% in Stage B, 54% in Stage C and 51% in Stage D) 9 . Even in bronchiectasis patients, the UK National Audits 2010 (n=1460) and 2011 (n=2404) revealed that ICS are used in 78–81% with a mean dose of 1094–1252 μ g/day 10 , despite BTS National Guidelines recommending not for routine use.

Recent study by Contoli et al assessing the effect of LABA-ICS vs. just a LABA on bacterial and viral loads in patients with moderate COPD showed an increase in bacterial load for

patients treated with ICS. However post hoc analysis indicated that this change was driven in patients with eosinophil counts of $\leq 2\%$ in peripheral blood¹¹.

This study therefore has selected this subgroup of severe COPD (GOLD 2017 classification Stage D) with a co-diagnosis of bronchiectasis as a cohort with the highest risk of infection. The aim is to explore the impact of inhaled corticosteroids in this high-risk group. No similar study has been conducted to date from a PubMed search on the 17th of September 2020.

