2. STUDY OBJECTIVES

2.1 OBJECTIVES

2.1.1 Primary Objective

In patients with severe COPD and bronchiectasis, does the addition of inhaled corticosteroids:

- Alter the microbial load of pathogens?
 - o ICS beneficial effect would lead to an expected reduction in microbial load, with less significant bacterial loads (10 colony forming units/ml or more).
 - o ICS detrimental effect, would lead to an expected increased microbial load, with significant bacterial loads (10 colony forming units/ml or more)¹².

This would be assessed between the two groups (LABA-LAMA-ICS and LABA-LAMA arms).

2.1.2 Secondary Objectives (between two arms of the study) to assess if ICS:

- 1. Are beneficial, patients will have a broadened microbial diversity in sputum microbiata and if detrimental there would be loss of this diversity¹³⁻¹⁵.
- 2. Alter sputum colour, airways and systemic inflammation. The mechanism of inhaled corticosteroids is anti-inflammatory, and the hypothesis is that inhaled

corticosteroids might improve sputum colour and reduce sputum and serum inflammation¹².

- 3. Impact on microbial and mycobial community composition as explained in endpoints section 2.
- 4. Impact on spirometry (forced expired volume in 1 second, forced vital capacity, its ratio and mid expiratory flows FEF25-75).
- 5. Impact on health status using well-validated quality of life questionnaires in bronchiectasis (COPD Assessment Tool¹⁶ and St George's Respiratory Questionnaire¹⁷).
- 6. Moderate/ severe exacerbation rate and time to first moderate/ severe exacerbation.
- 7. Investigate if addition of inhaled corticosteroid has an overall beneficial/detrimental effect to the mortality rate and whether that correlates with the microbial diversity that we are also assessing in these 2 groups.

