3. STUDY DESIGN

TEMPESTAS is a multi-centred, open label, parallel group randomised study across between 3 - 6 sites. We plan to recruit 80 patients.

To optimise the airflow limitation, we are treating all patients with a combined LAMA and LABA for a washout period of 4 weeks ANORO ELLIPTA 1 puff once daily (combination of umeclidinium 55mcg and vilanterol 22mcg once a day) and the study drugs selected are first line on all our formulary.

These patients will then be randomised in a 1:1 ratio to LABA-LAMA or LABA-LAMA plus additional inhaled corticosteroids (Trelegy Ellipta 92/55/22 I puff once a day). All treatment durations then would last for a year.

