3.9.3 Washout

Patients must satisfy the study inclusion and exclusion criteria, as possible at this stage during the screening visit to be eligible to receive the washout medication. Eligible patients will be asked to stop their regular inhaler therapy and will receive Anoro Ellipta 55/22 mcg one puff once a day (Long-acting beta agonist/long acting antimuscarinic) for 4 weeks.

Only participants who are eligible for and agree to the 4-week washout will be entered into the eCRF and allocated a trial number.

Patients who do not adhere to the washout treatment regime or do not tolerate the washout medication will be ineligible to be randomised and their participation in the study discontinued.

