3.11 RANDOMISATION

3.11.1 Randomisation Procedures

Following successful completion of the 4-week washout phase, verbal reaffirmation will be sought from the patient and recorded in the medical records to collect the baseline data necessary to complete the randomisation and the exclusion criterion would be rechecked.

If still eligible, the participant would be randomised to one of the two arms of the study triple (inhaled corticosteroids/Long-acting beta agonist/long acting antimuscarinic arm) or dual bronchodilator (Long-acting beta agonist/long acting antimuscarinic arm) therapy. Allocation will be made in a 1:1 ratio of study triple: dual bronchodilator using a minimisation algorithm stratified on the following variables: prior ICS (yes/no) and prior long-term macrolides (yes, no). In order to maintain a random allocation, participants will be allocated to the group which minimises the imbalance with a pre-defined probability.

The Investigator will enter the participants data via a 24-hour secure centrally controlled web based GCP compliant central randomisation system, run by the UKCRC registered Edinburgh Clinical Trials Unit (ECTU) using a validated randomisation program and will securely backup both the randomisation seed and the randomisation allocation.

The randomisation system will provide details of the treatment allocation and a confirmatory email will be sent to the PI, RN and local Clinical Trials Pharmacy. The Trial Manager and CI will receive confirmatory treatment allocation emails for all participants at all sites.

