Results will be presented broken by treatment allocation. Where data is categorical number and percent will be presented however where data is continuous descriptive statistics including mean, standard deviation (sd), median, q1, q3, min, max will be presented. As this is a proof-of-concept study we will present descriptive statistics for markers of interest by treatment arm at each time point as well the baseline to 1-year change. No covariates are planned to be adjusted for these analyses.

Where responses are continuous for example the level of change in cfu, comparison between groups will be made using a two-sample t-test and results of this will be presented accompanied by the mean and 95% for the difference between groups. We will present the time to first exacerbation using a Kaplan-Meier survival curve stratified by treatment allocation and present this will the accompanying log-rank statistic.

Where responses are binary i.e., presence of clinically significant change in cfu, comparisons between groups will be made using a binomial test for the comparison of proportions and accompanying this we will present the difference in proportion and 95% CI for the difference.

The number of participants experiencing adverse events and serious adverse events will be reported as well as the number of events per participant. Comparison will be made between treatment arms. As information on AE/SAE will be captured during the washout phase prior to any dosing with study drug we will present this information separately for AE/SAE occurring prior to the first dosing and AE/SAE occurring after the first dosing.

Dropouts during the study will be reported and where available a reason for dropout will be captured. The dropout rate will be compared across both treatment arms

16S and ITS data: we will summarise and visualise microbial and fungal community compositions using ordination techniques/PERMANOVA-tests, allowing for global comparisons between groups. To compare alpha diversity between samples, we will look at the richness, as well as the Shannon

Version No 2.1

Effective Date 27Jun2025

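### The primary t-test ignores prior ICS, a minimisation factor: it is valid on average, but cannot show whether the effect differs by prior use and may be conservative

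*SAP*

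**What the plan says.** - **Question.** Protocol 2.1.1 asks "does the addition of inhaled corticosteroids" alter microbial load, and says this is assessed between the LABA-LAMA-ICS and LABA-LAMA arms.
- **Run-in.** Under Protocol 3.9.3, "Eligible patients will be asked to stop their regular inhaler therapy", and everyone takes LABA-LAMA for 4 weeks. Protocol 6.2 lists sputum collection at the baseline visit, after that period.
- **Allocation.** Protocol 3: "These patients will then be randomised in a 1:1 ratio to LABA-LAMA or LABA-LAMA plus additional inhaled corticosteroids". Protocol 3.11.1 uses a "minimisation algorithm stratified on the following variables: prior ICS (yes/no) and prior long-term macrolides (yes, no").
- **Primary analysis.** SAP 4.4 states that the baseline to 1-year log change "in colony forming units per ml will be analysed using a two-sample t-test", comparing the two arms.
- **Adjustment.** SAP section 2, repeating Protocol 8.2: "No covariates are planned to be adjusted for these analyses".
- **Use of prior ICS.** After the description of allocation in the SAP introduction, prior ICS appears only in SAP 4.3, as a table of its distribution by arm. No adjusted, stratified, subgroup or interaction analysis of the primary outcome by prior ICS is planned.

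**The concern.** Participants reach randomisation by different routes. Someone who used ICS before the trial has had it stopped 4 weeks earlier and is then allocated either to stay without it or to receive it again. Someone who did not use it is allocated to start it or not. The response of the airway flora could differ between these groups. The sponsor thought prior ICS important enough to make it one of only two minimisation factors, yet the outcome analysis does not use it.

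Two things are at stake:

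- **Interpretation.** If the effect differs by prior use, the pooled mean is a weighted average whose weights are the shares recruited. A reader could not tell a uniform modest effect from a large effect in one group and none in the other.
- **Efficiency.** If prior ICS predicts the change in bacterial load whatever the arm, balancing on it and then ignoring it leaves its variance in the standard error. The test then rejects less often than its nominal level.

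**Working it through.** **Inputs.** From Protocol 8.1: 36 evaluable per arm, difference 0.76 log, SD 0.98 log, two-sided 5%, 90% power, 10% dropout. The documents do not give the trial's share of prior ICS users. I assume 51% to 81%, from two figures in Protocol 1.1: a multinational COPD survey ("54% in Stage C and 51% in Stage D") and UK bronchiectasis audits (78–81%). Neither source describes this trial's population.

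**1. The plan's own figure.** Standard error of the difference = 0.98 × √(2/36) = 0.231, so 0.76/0.231 = 3.29. Noncentral-t power with 70 degrees of freedom is 90.1% at 36 per arm. Dropout: 72/0.9 = 80. The sample size reproduces.

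**2. Is the pooled estimate biased?** No. In simulation (10,000 runs per scenario, strata balanced across arms), equal effects of 0.76 in both groups return a mean estimate of 0.76. With 0.76 in non-users and 0 in users, the mean estimates are 0.38 (51% users) and 0.15 (80% users). Both equal the true average effect over the mix.

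**3. How far the mix could move the pooled figure.** Illustration only: the effect is 0.76 in one group and 0 in the other. The pooled difference is 0.76 × (share with the effect). Power is noncentral t with SD 0.98.

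| Effect only in | Prior-user share | Pooled difference | Power |
|---|---|---|---|
| prior ICS no | 51% | 0.76 × 0.49 = 0.37 | 35.6% |
| prior ICS no | 81% | 0.76 × 0.19 = 0.14 | 9.5% |
| prior ICS yes | 51% | 0.76 × 0.51 = 0.39 | 38.0% |
| prior ICS yes | 81% | 0.76 × 0.81 = 0.62 | 74.8% |

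**4. Cost of not adjusting if prior ICS is prognostic.** Assumption: users and others differ by 1 log in mean change in both arms, and 0.98 is the SD within each prior-ICS group. With the factor balanced, the estimate's true standard error stays at 0.231. The t-test, however, uses the within-arm SD, which includes the gap between groups.

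- 18 users and 18 others per arm: SD = √(0.98² + 0.257) = 1.103. The effective critical value is 1.994 × 1.103/0.98 = 2.25 instead of 1.99.
- 29 and 7 per arm: SD = √(0.98² + 0.161) = 1.059. The effective critical value is 2.16.

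Here 0.257 and 0.161 are (users × others/36²) × (36/35) × 1². The simulation gives:

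| Prior-user share | Type I error, unadjusted | Type I error, adjusted | Power at 0.76, unadjusted | Power at 0.76, adjusted |
|---|---|---|---|---|
| 51% | 2.8% | 5.0% | 85.0% | 90.3% |
| 80% | 3.4% | 4.9% | 87.5% | 90.7% |

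With no prognostic difference and the same effect in both groups, adjustment changes nothing material (90.5% against 90.5%; 90.1% against 90.0%).

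**5. Precision of a split by prior ICS.** Stratum half-width = t × 0.98 × √(2/n), with n per arm. For the interaction, half-width = t × 0.98 × √(2/n₁ + 2/n₂), with 68 degrees of freedom and t = 1.995.

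- 51% share (18 and 18 per arm): 2.032 × 0.98 × √(2/18) = 0.66 in each stratum. Interaction: 1.995 × 0.462 = 0.92.
- 81% share (29 and 7 per arm): 2.003 × 0.98 × √(2/29) = 0.52 for users and 2.179 × 0.98 × √(2/7) = 1.14 for others. Interaction: 1.995 × 0.584 = 1.16.

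By the normal approximation, power to detect an interaction of 0.76 log is 38% at a 51% share and 25% at 81%.

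**The case against.** The strongest objection is that the pooled comparison is exactly what the protocol asks for. Everyone is on LABA-LAMA alone at randomisation, the objective names the between-arm contrast, and ICS was stopped before allocation in both arms. Carry-over from earlier ICS is therefore shared. It may modify the effect, but it does not bias the difference. This stands. A reader might infer that the pooled result mixes two different contrasts and so cannot answer a question about adding ICS, or that statements about addition belong only to participants without prior ICS. The documents do not support either reading. The second would also replace a randomised comparison planned at 90% power with a stratum of about 7 to 18 per arm.

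Three further points stand:

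- The factor is a yes/no flag with no look-back period, dose or duration, so "no" does not establish that a participant is ICS-naive.
- The documents offer no evidence that prior ICS modifies the effect. The modifier that Protocol 1.1 reports from an earlier study is a blood eosinophil count of 2% or less.
- The low power in step 3 reflects a smaller average effect. It is not a fault of the t-test.

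It can also be said that a proof-of-concept trial may keep its analysis simple, and that minimising on a factor does not oblige anyone to report subgroups. That is fair as far as subgroups go. It does not answer the efficiency point: analysing by a factor already balanced in the design costs almost nothing and protects the nominal error rate. Imprecision is a reason to label the split exploratory, not to leave it out.

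**Conclusion.** The point holds as an improvement to the analysis. It is not a flaw that invalidates the primary result. The pooled t-test estimates the average effect of allocation to added ICS without bias. What the plan lacks is any means of seeing whether that average conceals a difference by prior ICS, and any use of the minimisation factors in the test.

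The loss from not adjusting is modest and conditional: type I error of about 3% instead of 5%, and power of 85% to 87% instead of 90%. This assumes a 1-log prognostic difference, exact balance of prior ICS across arms, and 0.98 as the SD within prior-ICS groups. A smaller prognostic difference means a smaller loss. Prior macrolide use was not modelled.

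The dependence on mix could be large (a pooled difference anywhere from 0.14 to 0.62 log in step 3), but only under the extreme assumption of no effect in one group, and only with prior-user shares taken from other populations.

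**What to change.** In SAP 4.4:

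1. Adjust the treatment comparison of log CFU change for prior ICS and prior long-term macrolides, for example with a linear model that has terms for treatment and the two factors. Amend the no-covariates statement in Protocol 8.2 and SAP section 2 to match.
2. Report the treatment difference within prior ICS yes and prior ICS no, with 95% CIs, and a treatment-by-prior-ICS interaction estimate with its CI, all labelled exploratory.
3. State the expected precision: half-widths of about 0.5 to 1.1 log within strata and 0.9 to 1.2 log for the interaction, assuming a 51–81% share of prior users.
4. Describe the overall result as the effect of allocation to an ICS-containing inhaler after a 4-week ICS-free run-in.

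The cost is SAP wording, the matching change to the protocol and one extra table. The flag is already collected for randomisation, so no new data are needed. The change should be fixed before the final analysis so that the split is not post hoc. The downside is that the stratum and interaction estimates will be imprecise, and a wide interval must not be read as evidence that the effect is the same in both groups.

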4.5 Secondary Outcomes

4.5.1 Sputum

Table showing the number and percent of participants with a of clinically significant change in CFU at 12 months compared to baseline split by treatment allocation. Where a clinically significant change in CFU is defined as a difference of 1 log (CFU /ml). Comparisons between treatment allocation will be made using a binomial test for the comparison of proportions and accompanying this we will present the difference in proportion and 95% CI for the difference.

For each of the following markers we will perform a comparison between treatment arms for baseline to 1-year change will be analysed using a two-sample t-test. Descriptive statistics will be presented by treatment arm at each time point in addition to the baseline to 1-year change, and the pattern of change over time shall be presented graphically.

- Sputum microbial diversity although stipulated as an endpoint in the protocol this information is not available and will not be presented in the statistical analysis.
- Microbial biomass expressed as quantified by 16S rDNA pg/ml

